### 3.5 Study Schema

Patients meeting criteria who have consented will be randomized to either control or CCH x 6 months, followed by a cross-over phase where controls will receive CCH. See Figure 1 for full study schema.

1. Control. Men in this cohort would undergo baseline assessments followed by no treatment for 6 months and then repeat assessments. Men would then cross-over to the CCH treatment phase and undergo up to 8 injections (or until curvature is <15 degrees, whichever comes first). Final assessments would then be performed 6 weeks following the final injection.
2. CCH followed by observation. Men in this cohort would undergo baseline assessments followed by up to 8 injections of CCH (or until curvature is <15 degrees). Assessments would then be performed 6 weeks after completion of treatment. Men then would not undergo any additional treatments for 6 months, after which they would have final assessments performed.

The following table provides an overview of the objective and subjective questionnaire administration:

	Baseline	1 st CCH of each series	6-weeks after CCH completed	End of no treatment phase
Baseline disease specific questionnaire	X			
Baseline subjective questionnaire	X			
IIEF	X	X	X	X
PDQ	X	X	X	X
1 st injection Xiaflex questionnaire		X	X	

Post Xiaflex subjective questionnaire			X	
Post no treatment subjective questionnaire				X
Length measurement	X	X	X	X
Curve measurement	X	X	X	X
Penile ultrasound	X			

### 3.6 Randomization Protocol

Following enrollment and completion of the consent, a length and curvature assessment will be performed as well as baseline questionnaires. Men will then be randomized based on a previously created randomization table that takes into account baseline curvatures (see attached Randomization Table). Groupings are divided based on initial curvature of 30-44, 45-59, 60-74, 75-89, 90 or above to assure equal representation in each study arm. Men will then undergo treatment as noted above.

## 4 Study Procedures

### 4.1 Screening Assessments

- Potential patient questioned to assure that they meet all inclusion / exclusion criteria
- Participant consented

### 4.2 Assessments

- Please refer to the table schema above (Section 3.5) for details as to timing of questionnaire administration.
- Objective measurements
  - Penile length obtained (pubic symphysis to corona and tip) – obtained by two separate providers with experience in PD therapies
  - Erection induced with alprostadil (dose to be determined by PI, with a goal to achieve a penetration-quality erection).
  - Curvature assessed in two planes as well as with photography (obtained in two planes)
  - Penile ultrasound performed to evaluate for plaque calcification. Plaques classified as none, mild (stippling), moderate (shadowing), and severe (>1 cm).
- Questionnaires

- Baseline disease specific questionnaire
- Baseline subjective questionnaire
- IIEF-15
- PDQ
- 1st injection Xiaflex questionnaire
- Post Xiaflex subjective questionnaire
- Post no treatment subjective questionnaire
- Adverse events (completed by study personnel only – not completed by study subjects)

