**Study Summary**

Title	Efficacy of a Novel Collagenase Clostridium Histolyticum Protocol for Peyronie's Disease Among Prior Non-responders: A Randomized, Controlled, Single-blinded Study
IRB Protocol Number	20213914
Methodology	Prospective, randomized, controlled, single-blinded
Overall Study Duration	2 years
Subject Participation Duration	1 year
Objectives	Compare key clinical outcomes between controls and men treated with a novel CCH protocol among men previously unresponsive to CCH administration.
Number of Subjects	40
Diagnosis and Main Inclusion Criteria	Men >18 years of age with Peyronie's Disease, current curvature of 30 degrees or more, prior treatment with 6-8 injections of CCH, and prior minimal (<20% and/or <10 degrees) responsiveness to CCH administration.
Randomization	Patients will be randomized 1:3 to control (no treatment) or CCH (up to 8 injections). Patients in the control arm will subsequently be crossed over to CCH treatment after 6 months. Randomization tables will be created and pre-stratified based on baseline penile curvature.
Follow-up Period and Assessments	Men will have objective assessments of curvature and length and standardized and non-standardized questionnaires obtained at various time points (baseline, 6-weeks following completion of CCH, and at the end of the no treatment phase).
Statistical Methodology	Stratification of subjects prior to randomization to assure an equal representation based on baseline penile curvature (30-44, 45-59, 60-74, 75-89, 90 or above). Statistical comparisons between groups and to baseline will be made of responses to subjective questionnaires and objective measures.
Plan for Publication	It is anticipated that the primary study will be published following accumulation of data out to 1 year. Pending novelty of findings, additional studies may also be published if felt to be warranted (subset analyses).

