### 1.2 Investigational Treatments

The current study would randomize men 1:3 into one of two treatment cohorts: 1. Observation followed by CCH or 2. CCH followed by observation. This study design offers the benefits of a randomized,

controlled trial (highest level of evidence), while also providing data for a second set of publications evaluating the cross-over to treatment phase (for controls). RCTs are particularly important in PD, where the disease changes over time in a percentage of men as a function of its natural history. This would also allow blinding of measurements using photographs (single-blinded assessments), which provides further study rigor. See Figure 1 for overall study schema.

1. No treatment (control) followed by CCH. Men in this cohort would undergo baseline assessments followed by no treatment for 6 months and then repeat assessments. Men would then cross-over to CCH treatment and undergo up to 8 injections (or until curvature is <15 degrees). Interval assessments would be performed with the 1st injection of each series, and final assessments would then be performed 6 weeks following the final injection.
2. CCH followed by no treatment. Men in this cohort would undergo baseline assessments followed by up to 8 injections of CCH (or until curvature is <15 degrees). Interval assessments would be performed with the 1st injection of each series and 6 weeks following completion of treatment. Men then would not undergo any additional treatments for 6 months, after which final assessments would then be performed.

During CCH administration, several key differences from the IMPRESS protocols would be performed. Please note that each of these changes have been slowly implemented in the investigators' practice over time to improve overall efficacy of therapy:

	IMPRESS Protocol	Current Study Protocol
Amount administered	0.58 mg	0.9 mg
Suspension volume	0.37 ml	0.7 ml
Method of injection	Into plaque	To point of maximal curvature in the tunica, as determined with an erection at the first injection of each series
Administration schedule	1-3 days apart	1 day apart
Mechanical device traction	None	RestoreX 30-60 min daily until 6 weeks after final injection
Office modeling	Performed 1-3 days after initial injections (defined as "firm")	10-15 lbs of force performed at the time of 2 nd injection

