### **2.2 Secondary Outcomes**

1. Compare IIEF outcomes between control and treatment groups at 6 months
2. Compare penile curvature changes in control men at baseline and 12 months (i.e. prior to and following cross-over to CCH)
3. Compare penile length changes in control men at baseline and 12 months (i.e. prior to and following cross-over to CCH)
4. Compare PDQ changes in control men at baseline and 12 months (i.e. prior to and following cross-over to CCH)
5. Compare IIEF changes in control men at baseline and 12 months (i.e. prior to and following cross-over to CCH)
6. Compare penile length changes between control and treatment groups at 6 months
7. Report adverse events at 6 and 12-month time points

8. Report changes in penile curvature between 6 and 12-month assessments for CCH men

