### **8.2 Conflict of Interest**

[name] is the inventor and developer of the RestoreX® device. His conflict has previously been reviewed with the Mayo Clinic Conflict of Interest Review Board, and following review, it has been determined that [name] is able to conduct clinical studies as a Primary Investigator (IRB17-001283).

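### Neither of the two providers who measure penile length by hand is masked to arm, so the between-arm length comparison (secondary outcome 6) is open to observer bias

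*Combined protocol and SAP*

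**What the plan says.** The Study Summary describes the methodology as "Prospective, randomized, controlled, single-blinded". Section 1.2 is the only place that says what is masked: "This would also allow blinding of measurements using photographs (single-blinded assessments), which provides further study rigor".

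Section 4.2 lists the objective measurements. For curvature it has "Curvature assessed in two planes as well as with photography (obtained in two planes". For length, taken from the pubic symphysis to the corona and to the tip, the only requirement on the measurers is "obtained by two separate providers with experience in PD therapies". It does not say whether they know the arm, whether they read independently, whether either may also treat the man, or how two readings become one value.

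Length is used in secondary outcome 6 (section 2.2), "Compare penile length changes between control and treatment groups at 6 months", and in secondary outcome 3, which compares control men with themselves before and after cross-over. Baseline length precedes randomization: under section 3.6, after consent "a length and curvature assessment will be performed as well as baseline questionnaires", and allocation follows.

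The table in section 1.2 makes daily RestoreX traction part of the CCH regimen, while controls have no treatment in their first 6 months. Section 8.2 states that the investigator "is the inventor and developer of the RestoreX" device.

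**The concern.** A length taken by hand on the patient depends on the person taking it. If that person knows that one man has had injections and traction and another has had nothing, expectation can shift the follow-up reading without any intent. The baseline reading is protected because it comes before allocation, so any shift at follow-up passes in full into the change score that outcome 6 compares.

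Two features add to the exposure. One arm receives an active regimen that includes the investigator's own device, and the other receives nothing. All treatment is given by one clinician at one clinic (section 3.2), and nothing prevents the treating clinician from being one of the two measurers. A favorable length result could then be questioned on grounds that the data could not answer.

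**Working it through.** **Does the described masking reach length?**

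1. Masking applies to measurements made from photographs (section 1.2).
2. Photographs are listed under curvature only (section 4.2).
3. Length is read on the patient, by providers chosen for experience (section 4.2).
4. No other section describes masking of an assessor.

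So, as written, no length reading is masked.

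**Does having two providers help?** Write each follow-up reading in the CCH arm as true length + b + e, where b is a shift shared by readers who know the arm and e is random error. The mean of two such readings has expectation true length + b. Averaging shrinks the variance of e and leaves b unchanged.

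**Which comparisons are affected?** Outcome 6 compares arms, so masking the reader to arm can protect it. Outcome 3 is a before-and-after comparison within controls, all of whom have crossed over by the later reading, so masking to arm does not help there.

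**How large could the effect be?** The plan has no figure for length to reproduce. The SD in section 5.2 (16 degrees, or 27%) is for curvature. The following is therefore an illustration in units of the SD of length change, with the bias b assumed.

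- Inputs from the documents: 30 men with 6-month data and alpha 0.05 (section 5.2); 1:3 allocation (Study Summary). This gives 30/4 = 7.5 controls and 22.5 CCH men.
- Assumptions: two-sided equal-variance t-test, no true difference, bias b in one arm only. Section 5.2 states neither the test nor its sidedness.
- Standard error factor: √(1/7.5 + 1/22.5) = √(0.1333 + 0.0444) = 0.4216.
- Degrees of freedom: 30 − 2 = 28; critical value 2.048.
- Noncentrality: b / 0.4216. The false-positive rate is the probability that a noncentral t exceeds the critical value in either direction.

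| Assumed bias b (SD) | Noncentrality | False-positive rate, 7.5 vs 22.5 | False-positive rate, 10 vs 30 |
|---|---|---|---|
| 0 | 0 | 5.0% | 5.0% |
| 0.25 | 0.59 | 8.8% | 10.2% |
| 0.5 | 1.19 | 20.9% | 26.6% |
| 0.75 | 1.78 | 40.4% | 51.7% |

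The noncentrality column is for 7.5 vs 22.5. The last column takes all 40 men as evaluable (standard error factor 0.3651, 38 degrees of freedom).

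**The case against.** **The label is not contradicted.** Section 1.2 says what single-blinded means here, namely masked reading of photographs, and does not promise that every outcome is masked. This stands: the point is a gap in protection, not an inconsistency.

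**The stakes are modest.** Length is item 6 of 8 secondary outcomes, section 5.2 calls the study exploratory, and no power claim or decision rule rests on length. This stands and limits the weight of the point.

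**The percentages prove little.** They would hold for any unmasked outcome under the same assumed bias. This also stands: they show how sensitive a comparison of this size is, not how large the bias will be.

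**Curvature is not well covered either.** Section 1.2 says only that the design would allow masked photograph reading, and section 4.2 names no masked reader. That is true, and it matters more because curvature is a primary endpoint. It is a separate gap, however: for curvature the protocol at least names a route to masking, and for length it names none.

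**Two stronger readings are tempting.** A reader might infer that length is the outcome the investigator's device is meant to improve. The documents do not say so: section 1.1 reports its effect on curvature, and section 8.4 mentions only the length of an inserted penile prosthesis, which is not an outcome here. A reader might also infer that the inventor takes the length readings. The documents leave the measurers' identity open; they do not exclude it, but they do not state it.

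**Conclusion.** The point holds as a gap in the measurement procedure. Section 4.2 specifies no masking of the length readers, the photograph masking in section 1.2 does not extend to length, and outcome 6 therefore rests on post-randomization readings by people who may know the arm. The investigator's interest in a device used only in the CCH arm during the compared period is a reason to close the gap; it is not evidence that bias will occur. The size of any bias cannot be derived from the documents, and the tabulated rates hold only under the assumed biases and the assumed t-test. With a secondary outcome in an exploratory study, the change should be made because it is cheap, but the primary endpoints do not depend on it.

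**What to change.** Amend section 4.2 as follows.

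- Reserve one of the two existing providers as the length reader for each man. This person does not treat him and does not attend his CCH series visits, where length is also measured (section 3.5) and the arm would be obvious.
- The reserved reader measures length at baseline and at the comparison assessment. The schedule in section 3.5 has no common 6-month visit, so name the assessment for each arm: 6 weeks after CCH completion for the CCH arm, and the end of the no-treatment phase for controls.
- The reader is not told the arm, measures before the other provider and before seeing any arm-specific questionnaire, and records on a separate form.
- The value for outcome 6 is this reader's own change from baseline to follow-up, so that no change score mixes readers. A reading by the treating investigator or the device inventor is not used for outcome 6. The other provider's reading is kept as a reliability check.

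The cost is wording and scheduling, with no extra staff. There are four downsides. One reading is somewhat less precise than two, by an amount the documents do not allow us to calculate. Only one provider would measure length at interval visits, though no listed outcome uses those values. Masking may fail if the man reveals his arm. Outcome 3 is not helped.

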## **5 Statistical Plan**

### **5.1 Data Handling**

All data will be recorded either by the patient themselves or by the provider directly onto printed forms. Information will remain de-identified throughout the remainder of the study period and will remain on password protected, CURE PD servers.

After completion of the study, de-identified information will be shared with individuals associated with Endo Pharmaceuticals who may assist with portions of the data analysis and/or manuscript drafting if desired. No identifiable information will be sent.

### **5.2 Statistical Analysis**

The current study is considered exploratory in nature. Analyses will be performed using comparisons within and between patient cohorts. All captured data will be utilized as a point of comparison based on accepted standards (e.g. IIEF subdomains, PDQ subdomains, etc.). All data will be analyzed to determine if it is normative / non-normative and will be described and compared appropriately (mean, SD versus median, IQR).

Patients with partial missing data will have all available data included for analysis, with no attempts made to statistically replace missing variables. All data will be analyzed using an intent-to-treat analysis.

Adverse events will be reported as a total as well as compared between cohorts.

A power analysis was performed using historical data from another one of the investigators' RCTs to determine the standard deviation for control men between two sequential assessments. Results of absolute curvature improvements demonstrated a standard deviation of 16 degrees or 27% relative improvement. Using a 0.05 alpha threshold, power of 80%, and expected cohort size of 30 (assuming 30 with 6-month data) this would allow us to distinguish differences over 17 degrees or 29%. Given the investigators' current improvements of 60% with the investigators' preliminary data, we would expect this study to have sufficient power to demonstrate a clinically and statistically significant finding.

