## **2 Study Endpoints**

### **2.1 Primary Endpoints**

1. Compare penile curvature between control and treatment groups at 6 months
2. Compare PDQ outcomes between control and treatment groups at 6 months

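### Section 5.2 names no primary test or model, lets a normality look steer the comparison, and gives the stratification factor, baseline curvature, no covariate or stratum term; a pre-named ANCOVA would fix this for one degree of freedom.

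*Combined protocol and SAP*

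**What the plan says.** The first primary endpoint in Section 2.1 is "Compare penile curvature between control and treatment groups at 6 months". It does not say whether the comparison is of the 6-month value, the change in degrees or the percent change. For length, by contrast, Section 2.2 writes "Compare penile length changes between control and treatment groups at 6 months".

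Section 5.2 gives the analysis in one sentence: "All data will be analyzed to determine if it is normative / non-normative and will be described and compared appropriately", followed by a parenthesis that sets mean and SD against median and IQR. No test, model, effect measure or sidedness is stated. The power paragraph in the same section works from improvement, on two scales: "Results of absolute curvature improvements demonstrated a standard deviation of 16 degrees or 27% relative improvement".

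On baseline, Section 3.6 stratifies the randomisation: "Groupings are divided based on initial curvature of 30-44, 45-59, 60-74, 75-89, 90 or above to assure equal representation in each study arm". The Study Summary adds "Statistical comparisons between groups and to baseline will be made of responses to subjective questionnaires and objective measures". No section puts baseline curvature or its bands into the between-arm comparison as a covariate or stratum.

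Section 4.2 records curvature in two planes and by photographs in two planes. Of the photographs, Section 1.2 says "This would also allow blinding of measurements using photographs (single-blinded assessments), which provides further study rigor". No section says which reading is analysed. The table in Section 3.5 places the CCH arm's post-treatment assessment 6 weeks after CCH is completed, and the controls' assessment at the end of their untreated phase.

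**The concern.** Randomisation balances the arms on baseline curvature. An unadjusted test of 6-month curvature ignores that: the between-man spread in baseline stays in its standard error although stratification has largely removed it from the arm difference. Such a test is conservative and can lose power. A change score uses baseline, but only by subtraction, which fixes its coefficient at 1 whatever the data show.

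The test is also left to a look at the data. With 1:3 allocation, 30 evaluable men give about 30/4 = 7.5 controls, and 40 men give 10. A normality check on so few men is a poor guide to choosing a test, and it leaves the primary comparison unsettled until the data are seen. What is at stake is power at moderate effects and a modest excess of false positives if the scale is chosen afterwards.

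**Working it through.** **The plan's own figure.** Inputs from Section 5.2: SD 16 degrees or 27%, alpha 0.05, power 80%, 30 men. Solving the noncentral t for a two-sided test with 15 v 15 men gives 16.96 degrees and 28.6%, which round to the stated 17 and 29%. One-sided with 7.5 v 22.5 gives 17.2 and 29.0%, and two-sided with 10 v 30 gives 16.8 and 28.3%. The match is therefore not unique. It concerns arm sizes and sidedness, and says nothing about scale. The scale of the power statement comes from its wording, which refers to improvements.

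**Model for the check.** Let follow-up F = m + s(B - m) + e, with B the baseline curvature, m its mean and s the slope. The SD of change is held at the plan's 16, so Var(e) = 256 - (1 - s)² Var(B). Before any treatment effect:
- SD of level = √(s² Var(B) + Var(e))
- SD of change = 16
- ANCOVA residual SD = √Var(e)

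The documents give no slope, no spread of baseline curvature and no block size. These are assumptions: slopes 0.6 to 1, and three baseline shapes (uniform 30-90; a skewed shape starting at 30 with mean 48, SD 10; the same with mean 59, SD 20).

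Example, uniform 30-90, Var(B) = 60²/12 = 300:
- s = 1: level √(300 + 256) = 23.6; change 16; ANCOVA 16.
- s = 0.6: Var(e) = 256 - 0.16 × 300 = 208; level √(0.36 × 300 + 208) = 17.8; change 16; ANCOVA √208 = 14.4.

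**Power, constant 20-degree effect.** The 20 degrees is an assumption. It is close to 34% (the phase III mean in Section 1.1) of the 59 degrees implied by 16/0.27: 0.34 × 59 = 20.1. Simulation: 40 men, 1:3 permuted blocks of 4 within the five bands, 30 kept at random, two-sided 0.05, 8,000 runs per cell.

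| Baseline | Slope | Level | Change | ANCOVA |
|---|---|---|---|---|
| Uniform 30-90 | 1 | 48.1% | 80.5% | 79.6% |
| | 0.8 | 60.3% | 80.4% | 81.6% |
| | 0.6 | 73.5% | 82.0% | 87.7% |
| Mean 48, SD 10 | 1 | 68.1% | 80.0% | 79.3% |
| | 0.8 | 73.0% | 80.5% | 80.4% |
| | 0.6 | 77.5% | 81.2% | 82.4% |
| Mean 59, SD 20 | 1 | 41.2% | 80.8% | 79.9% |
| | 0.8 | 52.7% | 80.8% | 81.8% |
| | 0.6 | 71.1% | 82.6% | 89.7% |

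Blocks of 8 are within 2 points. Over all of these, ANCOVA is about 4 to 39 points above level, and about -1 to +7 points against change.

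**Power, proportional effect.** Sections 1.1, 1.3 and 5.2 express benefit as a percentage, so a constant shift is not the only plausible form. With a 34% effect and slope 0.6, level has 62-84%, change 60-74% and ANCOVA about 64-88%. Over slopes 0.6 to 1, ANCOVA is about 0 to 19 points above change and about 1 to 23 above level. The reason change suffers: at s = 0.6, a treated man's change has slope 0.6 - 0.34 - 1 = -0.74 on baseline. With baseline SD 20, Var(e) = 256 - 0.16 × 400 = 192, so the SD of change in the treated arm is √(0.74² × 400 + 192) = 20.3, against an error SD of √192 = 13.9. With a 60% proportional effect, all three analyses have at least about 96%.

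**No true effect.** Under stratified allocation the level test rejects about 1.5-5% of the time and ANCOVA about 5%. Reporting whichever of level, change or percent change is significant gives about 6-8%, or 7-9% if a rank test is also open.

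**The case against.** The strongest reply is that change is plainly intended. The power paragraph uses improvement and the Study Summary compares to baseline. On that reading baseline already enters the comparison, and for a constant shift ANCOVA adds little. This largely stands. A reader might infer that baseline plays no part at all between the arms, and the documents do not support that: a change score uses it by subtraction. What they support is that no covariate or stratum term is stated, and that change itself is never named as the primary measure.

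A second reply is that the sentence in 5.2 concerns summary measures only, given its parenthesis. That is possible. But the sentence also covers how data are compared, and nothing else in the plan names a test.

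A third is that the study is called exploratory and the hoped-for effect is large. This also stands: at 60% the choice hardly affects power. It lowers the severity but does not fill the gap, because Section 5.2 also expects a statistically significant result. The 60% comes from an unpublished series in which only several men had had prior CCH.

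Two further inferences should be resisted. One is that the false-positive rate would reach 10% or more: simulations without stratified allocation give up to 10-12%, but under the planned stratification it is about 6-8%. The other is that naming change as primary would do just as well: that holds for a constant shift in degrees, not for a proportional effect.

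**Conclusion.** The gap is real and should be closed. No primary test or model is named, a look at the data may steer the comparison, and the stratification factor has no covariate or stratum term. It is graded as an improvement the sponsor should make, not as a fatal flaw.

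The absence of the specification is certain from the text. The power figures are not: they rest on the assumed slopes, baseline shapes, block sizes and form of effect, and should be read as ranges. The 39-point loss arises only if Section 2.1 is applied literally as an unadjusted comparison of 6-month level, with slope 1 and widely spread baselines. Over the settings examined, ANCOVA was at most about 1 point worse than change and up to about 19 points better, and kept its error rate near 5%.

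**What to change.** In Section 5.2, make the primary analysis a linear model (ANCOVA) of follow-up curvature in degrees on randomised arm, with baseline curvature in degrees as a continuous covariate. Report the adjusted difference and its 95% CI. Use the same model for PDQ, with the baseline score of one named PDQ subdomain.

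State that no normality check selects the primary test. A rank test, or a permutation test within the curvature bands, can be a sensitivity analysis. Label change and percent change as descriptive, and word Section 2.1 to match.

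In the same edit, name the visit that supplies the 6-month value in each arm, since Section 3.5 ties the CCH arm's assessment to completion of CCH. Name also the curvature reading that enters the model, preferably the photograph-based blinded reading of Section 1.2.

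The cost is wording and one degree of freedom. Section 3.6 already has curvature measured in every man before randomisation, and Section 4.2 already has the photographs taken.

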### 1.3 Preliminary Data

Please refer to the introductory section for a more complete description of preliminary data. The investigators' team has been implementing the above, novel techniques in a step-wise fashion over time. Data from men who have been treated since Jan 2020 demonstrates a median improvement of ~60% (compared to 30% with prior series). Importantly, this series included several patients who had

previously undergone prior CCH injections with other providers. These findings suggest a proof of concept for the novel approach and would represent the largest improvement in curvature ever achieved with CCH. Findings would also benefit Endo Pharmaceutical, as it would provide proof of concept data that additional series of CCH may be merited in many cases of men with PD.

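### The detectable difference in 5.2 uses an SD from untreated men for both arms and, read two-sided, fits 1:1 rather than the planned 1:3 allocation

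*Combined protocol and SAP*

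**What the plan says.** Section 5.2 (Statistical Analysis) has one variance input. Data from another of the investigators' trials were used "to determine the standard deviation for control men between two sequential assessments", giving a "standard deviation of 16 degrees or 27% relative improvement". The design inputs follow: "Using a 0.05 alpha threshold, power of 80%, and expected cohort size of 30 (assuming 30 with 6-month data"). The result is that "this would allow us to distinguish differences over 17 degrees or 29" per cent. The plan then sets a 60% improvement from preliminary data against this figure and concludes that power is sufficient. Section 1.3 reports that 60% as a median, without SD, IQR or number of men: it "demonstrates a median improvement of ~60% (compared to 30% with prior series").

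The Study Summary gives the allocation: "Patients will be randomized 1:3 to control (no treatment) or CCH (up to 8 injections"). Section 3.4 plans up to 40 enrolled so that at least 30 have outcomes. Section 5.2 calls the study exploratory and leaves the choice of comparison to a normality check. It names no between-arm test, says nothing about equal or unequal variances, and does not say whether alpha is one- or two-sided.

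**The concern.** Two inputs to the power statement do not match the trial as designed.

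- **The SD.** It describes men who received no treatment. It is carried over without comment to the arm that will hold about three quarters of the analysed men. Men who receive an active treatment may respond unevenly, and the baseline range is wide ("Groupings are divided based on initial curvature of 30-44, 45-59, 60-74, 75-89, 90 or above"), so an equal spread in degrees needs a reason.
- **The allocation.** For a fixed total, a 1:3 split is less precise than 1:1, and 5.2 does not give the arm sizes it used.

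At stake is the stated sensitivity, which is what a reader would use to interpret a difference smaller than expected. There is a second, conditional risk. With unequal arms and unequal SDs, a pooled-variance t-test does not hold its nominal error rate, and 5.2 neither chooses nor excludes that test.

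**Working it through.** **Inputs.** Alpha 0.05, power 80%, 30 men with data, and control SD 16 degrees or 27% (all 5.2); allocation 1:3 (Study Summary). Since 30 × 3/4 = 22.5, the arms are about 22:8 or 23:7. Assumptions: two-sided testing unless stated, and a treated SD, which the documents do not give.

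**Step 1: reproduce the stated figure.** With a common SD, SE = SD × √(1/n₁ + 1/n₂). The detectable difference is the value at which the noncentral t gives 80% power.

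| Arms | Sides | SE (degrees) | Detectable difference |
|---|---|---|---|
| 15:15 | 2 | 16 × √(2/15) = 5.84 | 16.96 degrees / 28.6% |
| 22:8 | 2 | 6.61 | 19.2 degrees / 32.4% |
| 23:7 | 2 | 6.91 | 20.1 degrees / 33.8% |
| 22.5:7.5 | 1 | 6.75 | 17.2 degrees / 29.0% |
| 30:10 | 2 | 5.84 | 16.8 degrees / 28.3% |

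The plan's 17 degrees and 29% are reproduced by 15:15 two-sided. The 30:10 row has the same SE because 1/30 + 1/10 = 2/15, but it needs data from all 40 men. Every row that fits uses the control SD in both arms.

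**Step 2: power at 17 degrees, two-sided, equal SDs.** It is 80% at 15:15, 70% at 22:8 and 66% at 23:7.

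**Step 3: let the treated SD vary (assumed), 22 CCH and 8 control, control SD 16.** For the Welch test, SE = √(SD_T²/22 + 16²/8) with Satterthwaite degrees of freedom. For example, a treated SD of 20 gives √(18.18 + 32) = 7.08 and a detectable difference of 21.2 degrees. The last column is the simulated two-sided error of a pooled t-test at nominal 5%, with equal means.

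| Treated SD | Welch detectable difference | Pooled-test error |
|---|---|---|
| 12 | 19.3 | 8.6% |
| 16 | 20.1 | 5.0% |
| 20 | 21.2 | 3.0% |
| 24 | 22.5 | 2.1% |
| 30 | 25.0 | 1.2% |

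The Welch test stays between 4.9% and 5.2%. Power at 17 degrees for treated SD 16, 20 and 24 is 66%, 61% and 56% with Welch, and 70%, 56% and 42% pooled.

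On the relative scale, if the treated-to-control SD ratio is the same, the figures multiply by 27/16: 32.6%, 33.9%, 35.8% and 38.0% for ratios 0.75, 1, 1.25 and 1.5.

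**Step 4: why the pooled error moves.** At treated SD 20 the pooled variance is (21 × 400 + 7 × 256)/28 = 364. The pooled SE is √(364 × (1/22 + 1/8)) = 7.88, against a true 7.08, so the test is conservative. At treated SD 12 the pooled variance is 172 and the SE 5.41, against a true √(144/22 + 32) = 6.21, so the error is inflated.

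**The case against.** **A reader might infer that the 60% effect contradicts a common SD.** It does not. A median reported without spread does not fix a variance. Suppose baselines are uniform on 30 to 90 degrees (mean 60, variance 300; an assumption), every treated man has a mean improvement of 60%, and the relative SD is 27%. The treated SD is then √((60² + 300) × 0.27² + 0.6² × 300) = 19.8 degrees, against √((60² + 300) × 0.27²) = 16.9 for controls. The whole excess, 0.6² × 300 = 108, comes from baseline curvature. It appears only in degrees: on the relative scale, which 5.2 also reports, both arms have 27%. Adjustment for baseline would largely remove it. In addition, injections end once curvature is below 15 degrees (1.2 and 3.5), which could narrow the treated spread. The documents do not settle the direction.

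**A reader might infer that the planned analysis has the wrong error rate.** No equal-variance test is planned, and a Welch or rank test would fit the wording of 5.2. The risk is conditional on an unnamed choice. It also needs equal means with unequal SDs; if treatment changed nothing, the arms would share one distribution and the pooled test would keep 5%. Where treated men vary more, the pooled test is conservative, so the cost is power and not false positives.

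**The allocation mismatch is not certain.** Sidedness is unstated, and two of the calculations above that respect 1:3 come close to the stated figures.

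These objections limit the point. They do not supply a treated-arm SD or the arm sizes behind the 17 degrees.

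**Conclusion.** The point holds as a limited correction. The stated 17 degrees or 29% rests on an SD from untreated men applied to both arms. On the usual two-sided reading it also rests on 1:1 allocation. For 30 men at 1:3 with equal SDs, the figure is about 19 to 20 degrees (32 to 34%). Over an assumed treated SD of 16 to 30 degrees, the Welch figure at 22:8 is about 20 to 25 degrees. Even a treated SD of 12 gives 19.3, so no two-sided Welch scenario examined with 30 men reaches 17. The upper end depends on a treated SD of 30, which has no source in the documents.

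Much of the move away from 17 is allocation: equal SDs at 22:8 already give 19.2 with a pooled test and 20.1 with Welch.

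A reader might also infer that the trial is underpowered for the effect it expects. The figures do not support that. For a true difference of 60 percentage points, power at 22:8 is 88% pooled and 97% with Welch even if the treated SD is twice the control SD. What needs correcting is the stated sensitivity to smaller effects. In a study described as exploratory, this is a minor point.

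**What to change.** In 5.2:

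1. State whether alpha is one- or two-sided, and give the arm sizes expected with 6-month data under 1:3 (about 22:8).
2. Restate the two-sided detectable difference as about 20 to 25 degrees, or about 34% or more on the relative scale, over a treated SD of 16 to 30 degrees. Label that SD as assumed, or replace it with an SD from the preliminary treated series if one is available.
3. Name the between-arm analysis for curvature: a Welch t-test, or a regression adjusted for baseline curvature with heteroscedasticity-robust errors. Either avoids relying on equal variances, whichever way the SDs differ.

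The cost is a few sentences and a less favourable stated figure; no extra men or visits are needed. If the SDs are in fact equal, Welch gives up about 1 degree of sensitivity compared with a pooled test (20.1 against 19.2 at 22:8).
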